Selection Criteria: Focus groups, interviews, and usability testing will target English-speaking obese older adults (age ≥65 years and BMI ≥30kg/m²¹⁷ or waist circumference ≥88/102cm⁸⁵ in females/males). Excluded from eligibility are adults with severe mental or life-threatening illness, dementia, substance use, history of bariatric surgery, suicidal ideation, unable to provide consent/perform measures, or residing in a nursing home. Older adult participants in Aims 2 & 3 will require the presence of home Wi-Fi high-speed internet, medical clearance, have less than a 5% weight loss in the past 6 months, and be without advanced co-morbidity, exercise restrictions⁸⁸ or involvement in other research studies.

Screening/Consent: Subjects expressing interest will be mailed/mailed forms, evaluated by chart review to confirm eligibility, and those meeting criteria invited to an RA-led session to verify final eligibility, review and complete consent forms, and answer queries. Competence for consent will be assured by: no diagnosis of dementia (all Aims) and a Callahan score ≥4 (Aims 2 & 3). Written consent will be obtained before enrollment. The RA will obtain screening/baseline measures, and provide a list of contact details (see Human Subjects).

10. Aim 3 (Evaluate home-based MOWI): Conduct and assess the feasibility, acceptability, and potential effectiveness of a home MOWI: MOWI will be delivered via video-conferencing in the subject's home in a 3x per week, 26-week program from the CHA (in contrast to Aim 2) by: an individual dietitian-led weekly nutrition session; 2x/week physical therapist-led group exercise session⁶⁹; and Fitbit monitoring of activity. We plan 5 cohorts of 8 subjects n=40. In-person RA-led assessments will occur at 0, 4, 8, 12 and 26 weeks. Only one exercise session will occur during these weeks. A HIPAA-compliant Android tablet with video-conferencing software (Vidyo)¹²⁰ will be configured by the Telehealth team and can record sessions, allowing 10% to be viewed randomly by the PI for fidelity. Prior to each nutrition session at home, weight will be assessed using a Bluetooth scale.

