Data from the Amulet will be transmitted to a Wi-Fi- secure cloud-based repository via HTTP post, decrypted and stored on an Amazon virtual machine running a MySQL database. The data can be downloaded by the RA. Individual data in Aim 1b and 2 will be kept confidential, although sharing of information that is communicated in group exercise sessions cannot be kept confidential to other participants.

Survey data will be performed on RedCAP software and be encrypted per institutional policies. The Department of Bioinformatics through the Center for Translational Science Activities will facilitate this process. Additionally, any video-conferencing will be performed through the Vidyo or Zoom software platforms are encoded to transmit securely between participant and study staff. At the conclusion of each wave, any software and tablets will be erased and data will be expunged per IT policies.

Data from the fitness devices and their applications will be password protected, and only study personnel would have access to the complete data. All data from the EHR will be HIPAA-compliant. No PHI information will be relayed during any of these sessions. The investigators will discuss this with the eligible subjects and ensure they are fully aware of these minimal, but possible risks. The risk of a contact allergy with the fitness device is possible, although we anticipate this risk being quite low, and if indeed this does occur, a communication with the patient's primary care provider will be made. Should the contact allergy be significant, the patient will be treated symptomatically or withdrawn from the study.

Potential Physical and Psychological Risks to Individuals (including possible alternative treatments) and Mitigation of Such Risks.

The MOWI comprises of a multidisciplinary treatment strategy, including nutritional, behavioral, and physical interventions, augmented by Telehealth modalities (telemedicine, mHealth and remote sensing). The confidentiality of focus group or individual data cannot be guaranteed. We will encourage and ask our study participants not to share the information discussed within the session.

Physical activity interventions may lead to mild muscular fatigue or soreness but will be monitored in a setting by trained professionals. Risk of falling is elevated in older adults¹⁷⁸ and will need to be supervised. Physical activity is recommended, even in sedentary individuals who may be at risk for cardiovascular

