events^{179,180}. As such, primary care clinicians need to provide medical clearance for individuals to participate in this program. Injuries may occur while engaging in the physical therapy program which will be allayed by a graded approach to activity. As with all functional measures there are safety issues. Physicians are on site at the Dartmouth Center for Health and Aging at the time of these sessions all of whom are certified in cardiac life support. If at any time during the study, the patient expresses any unexplained physical symptoms, the RA or clinical staff will share this information with the PI, who in turn will contact the participant's primary care provider to ensure prompt evaluation. Should the primary care provider not be available, the participants will be transported, if deemed medically necessary, to the closest Emergency Department. A member of the study staff will remain with the participant until there is a safe transfer of care. For Aim 3, additional safety measures have been established to ensure the safety of participants while participating in at home exercise classes where an RA or physical therapist will not have direct contact with them at the time a physical symptom may arise. (See attached safety flowchart) Lastly, rarely during focus groups or semi-structured interviews would individuals become uncomfortable; however, they will be reminded that they are participating voluntarily and may leave the group at any time. Our Institution Review Board expects notification of any incidental findings, as well as about any unanticipated problems involving risk to subjects. Any newly identified psychiatric disorder will be referred to the primary care provider for assessment and treatment.

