Research participants have an opportunity to engage in a medically supervised Obesity Wellness Intervention using novel technologies and would benefit from the discussions with other participants in similar situations. For the intervention development, participants will participate in this program which has the potential to improve their overall function, aerobic and resistance activity and wellness. Approximately 150minutes weekly of aerobic physical activity is recommended^{166,167}. While our program focuses primarily on resistance training, we will encourage individuals to achieve the aerobic objective on their own. Individuals will obtain data that could potentially be used in clinical settings. The monetary appreciation is another benefit of this proposed research that will offset travel costs. The overall risks of this study are quite minimal, yet in line with recommendations from major medical societies. Obesity interventions are recommended even in older adults¹⁶⁸, yet we believe that any benefits received from this intervention far exceed those risks. The components of the obesity intervention would be considered medically necessary for older adults with obesity.

Importance of the Knowledge to be Gained

The information gained in this study will allow the investigators to ascertain the benefits from a technology-based wellness program and anticipate furthering our understanding of the implications of this program on functional and biological biomarkers. Understanding these relationships in a clinical setting will allow further refinement into a wellness program for obese older adults with the goal of limiting the acceleration of sarcopenia and improving function. The program engages and empowers patients in altering their lifestyle, thereby promoting healthy living, proper nutrition, physical activity, and maintenance of function. The risks of the study are minimal to individuals in relation to the potential benefits they may receive.

Additionally, the Amulet is intended on becoming a commercially available device intended on improving physical health and wellness. The device has been granted a Non-Significant Risk exemption (NSR) according to published intent of Amulet¹⁰⁰ and review of the protocol by the Committee for the Protection of Human Subjects at Dartmouth, dated 7/23/2015 based on 21 CFR 812.2(b)(ii) (Appendix).

Confidentiality and Data Integrity:

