
All information will be kept confidential during all phases of the intervention, including monitoring, preparation of interim results, review and response to monitoring recommendations. Monitoring will also consider external study factors when interpreting data, including scientific or therapeutic developments that can impact participants. The results of the trial will be forwarded upon publication of its results to all subjects at the conclusion of the intervention. The team will also provide the subject’s healthcare providers with appropriate information, as needed, concerning the individual.

Adverse Event Reporting

Serious, unexpected adverse events (SAE) related to study participation are anticipated to be rare. Study personnel will be trained to report all adverse events. In addition, screening for adverse events potentially related to the study intervention will occur during the routine administration of study assessment measures. These interview-based indicators will augment required SAE reports by study personnel, including specific items in the assessment interviews evaluating episodes of muscle or fall-related injuries, unexpected medical events, medical emergency room admissions, medical hospitalizations, or unplanned medical clinic

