visits. If an SAE occurs, the PI will report the event to the Dartmouth CPHS using the CPHS Adverse Event Form, to the DSMB, and to the NIA Program Officer within 10 days of the study's knowledge of the SAE (if unanticipated) unless otherwise requested by the DSMB. The PI, in consultation with co-investigators and others, as needed, will review the adverse event report and gather other information as needed to investigate the event and determine the need for subsequent action. Any subsequent action will be documented and reported to the CPHS. In addition, any SAE will also be reported to the NIH program officer and they will be informed of any actions taken by the CPHS as a result of its continuing review. The CPHS will review each reported adverse event to determine whether: the participants in the study should receive additional information related to continuing their participation; the protocol, study plan or consent form should be modified; or the study should be temporarily suspended. If the CPHS determines that some action in response to the adverse event is necessary, the CPHS will promptly inform the PI. All deaths will be reported in an expedited manner, normally within 24 hours of the study's knowledge. The report of death will also be submitted to the NIA Program Administrator and to the CPHS and to the DSMB Chair.

STATISTICAL DESIGN AND POWER

Aim 1 (*Qualitative assessment*) will use mixed-methods to adapt Amulet and MOWI for use in rural older obese adults. Aim 2 (*Develop/refine MOWI*) and Aim 3 (*Evaluate home-based MOWI*) will explore feasibility/acceptability, and preliminary effectiveness of the above outcomes. Data will be analyzed as follows:

Aim 3 (Evaluate home-based MOWI): Conduct and assess the feasibility, acceptability, and potential effectiveness of a home-based MOWI:

- Feasibility/Acceptability: Rates of screening, eligibility, enrollment, completion, assessment, entry criteria
- suitability, attrition reasons, satisfaction, acceptability, usability, and feasibility of MOWI will be assessed using mixed-methods at 26 weeks as in Aim 2.
- Statistical Analysis: The 1^o outcome of Physical Function and 2^o outcomes of behavioral activation, health status, and activity will be assessed and analyzed at 0, 4, 8, 12, 26 and 12-weeks post-study as in Aim 2.

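### In Aim 3 the structured adverse event questions go from every 4 weeks to one 14-week interval after week 12; asking them at existing nutrition sessions in weeks 16, 20 and 24 would keep the 4-week spacing

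*Combined protocol and SAP*

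**What the plan says.** Adverse Event Reporting sets out two layers. Staff are trained to report every adverse event. On top of that, "screening for adverse events potentially related to the study intervention will occur during the routine administration of study assessment measures". The items cover muscle and fall injuries, unexpected medical events, emergency and hospital use, and clinic visits that were not planned. They sit in the assessment interviews, and the section says that they add to staff reports.

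For Aim 3, section 10 states: "In-person RA-led assessments will occur at 0, 4, 8, 12 and 26 weeks". The programme lasts 26 weeks, is delivered by video to the home, and includes "an individual dietitian-led weekly nutrition session". That session already has a routine check attached: "Prior to each nutrition session at home, weight will be assessed using a Bluetooth scale". The Aim 3 part of Statistical Design and Power adds one later point, with outcomes "analyzed at 0, 4, 8, 12, 26 and 12-weeks post-study". The 12-week in-person programme used for Aim 2 is assessed at weeks 0, 4, 8 and 12.

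On risk, the plan says "Risk of falling is elevated in older adults", and under Potential Benefits it adds that "we will encourage individuals to achieve the aerobic objective on their own".

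**The concern.** The screen runs at 4-week spacing up to week 12 and then stops until week 26, although the home exercise programme carries on. A minor fall, a strain or an unplanned clinic visit in that period is recorded if the participant mentions it, if staff see it, or if the participant recalls it at week 26 over as long as 14 weeks. Exercise done alone between sessions is where an event is least likely to be seen.

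Two things are at stake. One is the quality and timeliness of minor-event data in an older group that the plan itself regards as prone to falls. The other is comparability: Aim 3 is meant to inform a larger study, and its event data would mix a 4-week and a 14-week recall window. In addition, a subject who leaves after week 12 and misses week 26 is never asked the items again. Reasons for attrition are collected, but they are not the same questions.

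**Working it through.** **Inputs**
- Aim 3 assessment weeks: 0, 4, 8, 12, 26 (section 10, Aim 3).
- Programme length: 26 weeks, with one individual nutrition session a week (same section). Assessment weeks reduce the exercise sessions; no reduction in nutrition sessions is stated.
- Structured items asked at assessments (Adverse Event Reporting). No available text schedules them at another contact.
- Aim 2 assessment weeks: 0, 4, 8, 12 (description of the MOWI programme).

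The plan gives no figure for the interval, so it is derived from the schedule.

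**Intervals as planned**
- 4 − 0 = 4; 8 − 4 = 4; 12 − 8 = 4; 26 − 12 = 14 weeks.
- Share of the programme in the last interval: 14/26 = 53.8%.
- The post-study assessment falls at week 38 if counted from week 26, so it does not shorten this interval.

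**Mean wait to the next scheduled form**, assuming a constant event rate (half the interval):
- Weeks 0–12: 4/2 = 2 weeks.
- Weeks 12–26: 14/2 = 7 weeks.
- Whole programme: (3 × 4²/2 + 14²/2)/26 = (24 + 98)/26 = 4.7 weeks.

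These are waits to the next form, not times to detection, because other routes may bring an event to light sooner.

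**Monthly reviews in the interval**
- 14/4.33 = 3.2, so about three meetings of the research assistant and principal investigator per cohort take place with no new structured answers from that cohort.

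**With added askings at weeks 16, 20 and 24**
- Intervals from week 12: 4, 4, 4 and 2 weeks. The longest is 4.
- Mean wait, weeks 12–26: (3 × 4²/2 + 2²/2)/14 = (24 + 2)/14 = 1.9 weeks, close to the 2 weeks before week 12.
- If the week-16 session is missed and the items are asked in week 17, the interval becomes 5 weeks.

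**Time needed**
- 3 × 40 = 120 askings. At an assumed 1 to 2 minutes each: 120/60 = 2 hours to 240/60 = 4 hours.

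**The case against.** The strongest case against acting is that the screen is only a supplement. Under the Data and Safety Monitoring Plan, a physician monitors adverse events during each session, and the research assistant and principal investigator review minor as well as serious events every month. Staff report all events. The risk section has its own trigger, "If at any time during the study, the patient expresses any unexplained physical symptoms", after which staff inform the principal investigator. Subjects are in video contact about three times a week. The risk section also cites an Aim 3 safety flowchart, and the monitoring plan cites a manual of procedures. Neither was available, and either could hold a symptom check at sessions. Aim 3 is a small single-arm pilot with low expected risk, so how often to repeat a questionnaire may be called a design preference.

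Most of this stands, and it limits the point. A reader might infer that Aim 3 has no safety surveillance for 14 weeks, or that events are being lost. The documents support neither reading: the other routes run to week 26, and no under-capture is shown. For the same reason the 7-week mean wait cannot be read as a delay in detection.

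What does not answer the point is that none of these routes is described as asking the structured items. Session monitoring is also harder at home: the risk section accepts that neither the research assistant nor the physical therapist will be in direct contact when a symptom arises in a home class.

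**Conclusion.** The point holds as a modest, inexpensive improvement. The supplementary screen goes from 4-week spacing to a single 14-week interval that covers 54% of the home programme. The consequences are a longer recall window, possibly later detection of events that nobody raises at a session, and no structured screen after week 12 for subjects who leave before week 26. The documents do not allow a useful estimate of how many subjects that would be.

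The intervals follow directly from the stated schedule. The mean waits also need a constant event rate. The conclusion would change if the flowchart or the manual already schedules these items between weeks 12 and 26.

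A reader might also infer that weekly questioning is required, since a weekly contact exists and the interval could fall to 1 week. The documents do not support that as the standard. The plan's own spacing is 4 weeks, a 1-week interval would need every session to be attended, and payment is tied to completing more than 80% of visits and assessments, so some absence is foreseen.

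**What to change.** Amend Adverse Event Reporting so that, in Aim 3, the same items are also asked at the nutrition video sessions in weeks 16, 20 and 24, or at the next session attended. Keep the screens at the assessments. Record the answers in REDCap, and pass them to the monthly review and to the regular DSMB reports. The longest interval during the programme then stays at about 4 weeks if sessions are attended, in line with weeks 0–12 and with Aim 2. If the flowchart or the manual already does this, a cross-reference is enough.

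The cost is one short form, one amended sentence, brief training for the dietitian, and 120 askings (2 to 4 staff hours on the assumption above). Logging and follow-up come on top. Under Adequacy of Protection Against Risks, any symptom that a participant endorses leads to immediate contact with primary care, and soreness is expected, so some extra contacts will follow. No visit or staff post is added. The added askings are by video and by the dietitian, whereas the assessments are in person and led by the research assistant, so ascertainment will not be identical.

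Weekly asking is optional. It would mean 26 × 40 = 1,040 askings (17 to 35 hours at 1 to 2 minutes) and would make event rates less comparable with Aim 2. If it were confined to weeks 13–25, rates would also be less comparable with Aim 3's first 12 weeks. Neither version covers the 12 weeks after the programme ends, when no nutrition sessions are planned.
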